1.4.1 Primary Endpoint

The primary endpoint of the clinical investigation is a composite endpoint at 90 days, including the following components representing important safety and effectiveness endpoints:

- Cardiovascular Death
- Myocardial infarction (MI)
- Stroke
- Any unplanned repeat revascularization (PCI or CABG)
- Bleeding (BARC 3 or 5) up to 14 days post-device removal
- Severe hypotension, defined as: systolic blood pressure (SBP) or augmented diastolic pressure (whichever is greater) <90 mmHg while on device support requiring (1) more than one administration of OR (2) continuous infusion of inotropic/pressor medications to restore hemodynamics
- Change in aortic insufficiency from baseline to 90 days by echocardiographic assessment and defined as:

| Baseline Assessment | 90 Day Assessment |
|---------------------|--------------------|
| None | Moderate OR Severe |
| Trace | Moderate OR Severe |
| Mild | Moderate OR Severe |

1.5 Randomization

1.5.1 Stratified Randomization

For the randomized cohort of the pivotal phase, up to 716 subjects will be randomized. Each site will be allowed a maximum of 60 randomized subjects. Subjects will be randomly assigned in a 2:1 fashion to either HeartMate PHP or Impella in SHIELD II.

[REDACTED]

1.5.2 Timing of Randomization

Randomization assignments will be given through EDC Study Site Portal after subjects have signed the ICF and met all eligibility requirements. Subjects will be considered registered in the clinical investigation once randomized and must follow all CIP requirements. Randomized subjects who do not undergo device placement due to previously undiagnosed anatomic abnormalities (e.g. peripheral vascular disease) which precludes device placement, will be considered registered and in the intent-to-treat (ITT) population, and they must follow all CIP requirements. Once a subject is randomized, PCI should be performed as soon as possible.

[REDACTED]

[REDACTED]

Statistical Analysis Plan

1.6 Blinding

This is an open-label clinical investigation. The subjects and the investigators will not be blinded to the treatment assignment. Nevertheless, measures of blinding will be taken to minimize bias and will be applied to the randomized cohorts of both the feasibility and pivotal phases.

[figure not shown]
2.0 ANALYSIS CONSIDERATIONS

2.1 Analysis Populations

All analysis populations will be applied to the randomized cohorts of both the feasibility phase and the pivotal phase. The two phases will be analyzed separately.

[figure not shown]
2.1.1 Intent-to-Treat (ITT) Population

The ITT population

[figure not shown]
2.1.2 As-Treated (AT) Population

The AT population

2.1.3 Per-Protocol (PP) Population

The PP population

Statistical Analysis Plan

2.2 Statistical Methods

Descriptive analysis will be performed to summarize baseline, hemodynamic measures, clinical and safety event data. Depending on the type of data (e.g., continuous or categorical), statistical methods described in the following sections will be used.

2.2.1 Descriptive Statistics for Continuous Variables

For continuous variables (e.g., age, etc.), results within treatment arm will be summarized with the numbers of observations, means, and standard deviations, with quartiles, minimums, maximums, and 95% confidence intervals for the means. Differences between the treatment arms, where specified, will be summarized with differences of the two means, and 95% confidence intervals for the difference between the means.

2.2.2 Descriptive Statistics for Categorical Variables

For binary variables (e.g. gender, diabetic status, etc.), results within treatment arm will be summarized with subject counts and percentages/rates, and where applicable, with exact 95% Clopper-Pearson¹ confidence intervals.

For events of interest, relative risks (i.e., the ratio of rates), confidence interval for the relative risks, the difference in rates and the confidence interval for difference in rates, and p-values may also be presented for hypothesis generating purposes.

For the determination of event rates, the denominators are defined as below based on the type of events.

- Primary endpoint event and its components

The denominator of the primary endpoint event rate will exclude subjects in the analysis population who terminated from the study [REDACTED] without a primary endpoint event or any subject who completes the 90-day follow-up without aortic insufficiency data at either baseline or 90-day follow-up and without a primary endpoint event. The same denominator rule will apply to individual component of the primary endpoint except for change in aortic insufficiency, which is an imaging endpoint and will follow the denominator rule set forth for missing data handling.

Statistical Analysis Plan

- Site-reported Adverse Events, Adverse Device Effects and Adverse Event related Descriptive Endpoints

[REDACTED]

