5.5 Subject Discontinuation

Each registered subject shall remain in the clinical investigation until completion of the required 90-day (\pm 30 days) follow-up visit however, a subject's participation in any clinical investigation is voluntary and the subject has the right to withdraw at any time

without penalty or loss of benefits. Conceivable reasons for discontinuation may include, but not be limited to, the following:

- Subject death
- Subject voluntary withdrawal
- Subject withdrawn by the Investigator
- Subject lost-to follow-up as described below
- Subject's follow-up is terminated according to **Section 3.3**.

The Sponsor must be notified of the reason(s) for subject discontinuation. The site will provide this information to the Sponsor. Investigators must also report this to their respective IRB as defined by their institution's procedure(s).

No additional follow-up will be required or data recorded from subjects once discontinued from the clinical investigation, except for the status (deceased/alive).

In case of subject withdrawal of consent, the site should make attempts to schedule the subject for a final clinical investigation visit prior to withdrawal. At this final follow-up visit, the subject will undergo the following assessments:

- Clinical assessment
- Echocardiographic assessment

Lost-to-Follow-up

There will be only one scheduled follow-up visit at 90 days (± 30 days) in this clinical investigation. If the subject misses the scheduled 90-day follow-up visit and the attempts at contacting the subject detailed below are unsuccessful, then the subject is considered lost-to-follow-up. Site personnel shall make all reasonable efforts to locate and communicate with the subject (and document these efforts in the source documents), including the following:

- A minimum of two telephone calls on different days over the specified follow-up window to contact the subject should be recorded in the source documentation, including date, time and initials of site personnel trying to make contact.
- If these attempts are unsuccessful, a letter (certified, if applicable) should be sent to the subject.

Note: Telephone contact with general practitioner, non-clinical investigation cardiologist or relative without the presence of the subject or indirect documentation obtained via discharge letters will not be considered as subject contact.

5.7 **Expected Duration of Each Subject's Participation**

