2.3 Endpoint Analysis

2.3.1 Primary Endpoint(s)

The primary endpoint, a composite of safety and effectiveness at 90 days, will be evaluated using the difference in event rates in the ITT population of the pivotal phase. The hypothesis test is designed to show non-inferiority of HeartMate PHP to Impella for the primary endpoint with one-sided alpha of 0.025.

[REDACTED]

ICER

[REDACTED]

If non-inferiority is met, superiority testing will be performed with a two-sided alpha of 0.05.

[REDACTED]

[REDACTED]

The data will be analyzed for superiority using Fisher's exact test.

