2.9 Handling of Missing Data

All analyses will be based on available data with missing data excluded.

[REDACTED]

[REDACTED]

Statistical Analysis Plan

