2.12 Sensitivity Analysis

The following sensitivity analyses of the primary endpoint will be carried out:

Worst Case Scenario Analysis

Tipping Point Analysis

Statistical Analysis Plan

Multiple Imputation

3.0 **DESCRIPTIVE ENDPOINTS AND ADDITIONAL DATA**

Data in the feasibility phase of the clinical investigation will be analyzed separately from data in the pivotal phase of the clinical investigation. Data collected for both roll-in and randomized subjects will be summarized descriptively. The results of the roll-in cohort will be analyzed as adjunctive data, separate from the results of the randomized cohort.

3.1 **Baseline and Demographic Characteristics**

The following baseline and demographic variables will be summarized: gender, age, height, weight, baseline risk factors, medical history, morphology, quantitative coronary angiography, echocardiogram, implant procedural characteristics, device usage, and quality of life, etc.

3.2 **Adverse Events**

The start of the index procedure will be a reference start time for summarizing all adverse events. All of the adverse device effects, serious adverse device effects, UADEs will be summarized for all subjects who registered in this trial in terms the number of events and the percentage of subjects with events.

All CEC adjudicated adverse events will also be summarized for all subjects who registered in the trial by treatment arms in terms the number of events and the percentage of subjects with events.

Statistical Analysis Plan

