3.3 Subject Early Termination

Subject early termination reasons including deaths, withdrawals, lost-to-follow-up, etc. will be summarized by treatment arms at the 90-day follow-up visit.

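### SAP 2.2.2 drops 90-day completers without aortic insufficiency data only when they are event-free, and carries that rule into clinical component rates where nothing is missing

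*SAP*

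**What the plan says.** SAP 2.2.2 sits under descriptive statistics, but it defines the denominator of the primary endpoint event rate. Two groups are excluded. One is early terminators without a primary event; that clause is partly redacted. The other is "any subject who completes the 90-day follow-up without aortic insufficiency data at either baseline or 90-day follow-up and without a primary endpoint event". The section then extends the rule: "The same denominator rule will apply to individual component of the primary endpoint except for change in aortic insufficiency".

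These rates feed the primary test. Under SAP 2.3.1 the composite "will be evaluated using the difference in event rates in the ITT population of the pivotal phase", at one-sided alpha 0.025. SAP 2.4 gives a 10-point margin, an assumed Impella rate of 20%, and 315 HeartMate PHP and 158 Impella subjects.

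On missing data, SAP 2.9 states "All analyses will be based on available data with missing data excluded". SAP 2.12 adds "The following sensitivity analyses of the primary endpoint will be carried out" and names worst-case, tipping-point and multiple-imputation analyses, whose details are redacted. SAP 3.2 separately summarizes adjudicated events for all registered subjects by arm.

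**The concern.** Two completers can lack the same echocardiogram and be treated differently. The one with a stroke counts in numerator and denominator. The one with no event is removed, although six of the seven components are known to be absent. Dropping only apparent non-events tends to push a rate up.

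For the composite there is some logic to this, because an event-free subject without AI data is not fully classified. For the clinical components there is none: a completer's stroke status is known whether or not the valve was imaged.

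At stake are the component rates, which are the main safety description of the device, the reported composite rate, and possibly the comparison with the margin if echocardiograms are lost unequally. SAP 1.6 says "The subjects and the investigators will not be blinded to the treatment assignment", so follow-up effort could in principle differ by arm.

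**Working it through.** **Inputs from the documents.** Impella rate 20%, margin 10 points, 315/158 subjects (SAP 2.4); one-sided alpha 0.025 (SAP 2.3.1).

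**Assumed.** Clinical-event rate c = 18% plus 2 points of AI-only events, making up the 20%. m = share of clinical-event-free completers who lack the required AI data, at 5%, 10% and 15%. A Wald test, because the actual test is redacted.

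The plan gives no figure for the effect of this rule. Its sample size of 473 cannot be reproduced, because the assumed PHP rate, power and attrition are not visible. Nothing below depends on it.

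**1. Who is kept.** For a completer without the required AI data:

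| Rate | Some primary event | No primary event |
|---|---|---|
| Composite | kept | removed |
| Each clinical component | kept | removed, although status is known |

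**2. Clinical components.** The numerator is untouched and the denominator loses m(1 − c) of subjects, so each rate is multiplied by 1/[1 − m(1 − c)].

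- m = 5%: 1/(1 − 0.041) = 1.04
- m = 10%: 1/(1 − 0.082) = 1.09
- m = 15%: 1/(1 − 0.123) = 1.14

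A true 2.0% stroke rate reads 2.2% at 10% missing. If the rule is instead applied to the component's own event, a 2% component gets 1/(1 − 0.98m) = 1.05, 1.11 and 1.17. Neither result needs an assumption about why echocardiograms are missing.

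**3. Composite, if one missing reading is enough.** With echocardiograms missing independently of AI status, the rate read is [0.18 + 0.02(1 − m)]/[1 − 0.82m].

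- m = 5%: 0.199/0.959 = 20.8%
- m = 10%: 0.198/0.918 = 21.6%
- m = 15%: 0.197/0.877 = 22.5%

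At m = 10% the upward bias disappears only if the removed subjects' hidden AI risk h reaches 21.6%, because the truth is 0.918 × 21.6% + 0.082h. The assumed AI risk is 0.02/0.82 = 2.4%, about one ninth of that.

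**4. Composite, if both readings must be missing.** A completer who lacks only the 90-day reading is then not removed by this clause. If such subjects make up 10% and count as event-free, a true 20% reads 0.18 + 0.02 × 0.9 = 19.8%, slightly low. The components in step 2 still read high, but m then covers only subjects lacking both readings.

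**5. The test.** Take a true difference equal to the margin: PHP 30% (27% clinical plus 3 points AI) against Impella 20%. The PHP rate read is [0.27 + 0.03(1 − m)]/[1 − 0.73m]. At 10% missing in both arms the difference read is 0.297/0.927 − 0.198/0.918 = 32.0% − 21.6% = 10.5 points from unrounded values, so the test becomes harder to pass. At 5% (PHP) and 15% (Impella) it is 31.0% − 22.5% = 8.5 points. Simulated false-claim rates (upper 97.5% Wald bound below 10 points):

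| Missing, PHP/Impella | False-claim rate |
|---|---|
| none | 2.2% |
| 5/5% | 2.0% |
| 10/10% | 1.7% |
| 5/8% | 2.5% |
| 5/10% | 3.1% |
| 5/15% | about 4.7% |

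A reverse gap costs power instead. At equal true rates of 20%, power is 74% with none missing, 67% at 10/10% and 52% at 15/5%. These figures show sensitivity only; they are not losses from the planned power, which is redacted.

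**The case against.** The strongest reply is that full-denominator reporting already exists. SAP 3.2 summarizes adjudicated events for everyone registered, and SAP 2.2.3 provides Kaplan-Meier estimates for time-to-event variables. Component rates are not separately tested. This stands as a limit on the harm: a reader will be able to find undistorted event percentages. It does not correct the component rates that SAP 2.2.2 itself defines, and two sets of percentages for the same events would then need explaining.

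Second, *either* is ambiguous, and step 4 shows that the direction of the composite bias depends on it. This stands, so an unconditional statement that the primary rate is inflated would go too far.

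Third, the missingness values have no anchor. The clause concerns subjects who completed a visit that includes echocardiography. Protocol 6.6 allows in-home echocardiograms, and Protocol 6.1 and 6.8 require inadequate pre-consent baseline studies to be repeated. This also stands; 10% to 15% is illustrative.

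A reader might infer that the rule endangers the non-inferiority conclusion or favors the investigational device. The documents do not support that. Equal missingness is conservative, gaps of 2 to 3 points barely matter, and the safeguards against missing echocardiograms apply alike to both arms. Open-label conduct makes a large gap possible, not expected.

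A reader might also infer the same bias for early terminators. Their clause is partly redacted, and Protocol 5.5 says "No additional follow-up will be required or data recorded from subjects once discontinued from the clinical investigation", vital status excepted. No size or direction can be claimed for them.

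**Conclusion.** The point holds, and it is minor. The firm part is the component rule: as worded, it removes subjects with known outcomes and overstates clinical component rates by a factor of about 1.04 to 1.14 at 5% to 15% missing on the any-event reading. Only the size depends on assumed missingness.

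The composite part is conditional. A true 20% reads about 20.8% to 22.5% if one missing reading is enough, echocardiograms are lost independently of AI status, and events split 18 plus 2.

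The test itself would be affected materially only by a between-arm gap of about 5 to 10 points, under an assumed Wald test. It would be tempting to conclude that imputation must become the primary analysis. That does not follow. It would be slightly less conservative in the expected case (false-claim rate 2.1% to 2.4% against 1.7% at 10/10%), would rest on a model for about 158 × 0.02 = 3 AI events in the Impella arm, and has no direct counterpart to the Fisher's exact test planned for superiority.

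**What to change.** Before unblinding:

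1. In SAP 2.2.2, keep every subject who completed 90-day follow-up in the denominator of each clinical component, whatever the echocardiogram status. Apply the AI-data condition only to the AI component and the composite.
2. State whether *either* means that one missing reading or both trigger exclusion.
3. Report missing baseline and 90-day AI readings by arm. SAP 3.3 already does the equivalent for dropout: "Subject early termination reasons including deaths, withdrawals, lost-to-follow-up, etc. will be summarized by treatment arms".
4. Present the multiple imputation listed in SAP 2.12 next to the primary result, keeping observed clinical events and imputing only AI status. Making it the primary analysis is the sponsor's option, not a required correction.

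Items 1 to 3 change wording and tables only, with no new data. Item 4 uses an analysis already named, though its redacted model may need adapting to few AI events.

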17. Active systemic infection requiring treatment with antibiotics
18. Subject had active COVID-19 symptoms and/or a positive test result within the prior 2 months.
19. Stroke or transient ischemic attack (TIA) within 6 months of procedure
20. Any allergy or intolerance to ionic and nonionic contrast media, anticoagulants (including heparin), or antiplatelet therapy drugs that cannot be adequately premedicated
21. Subject is pregnant (For a female subject of childbearing potential, a pregnancy test must be performed within 14 days (≤ 14 days) prior to the index procedure per site standard test).
22. Participation in another clinical study of an investigational drug or device that has not met its primary endpoint
23. Presence of other anatomic or comorbid conditions, or other medical, social, or psychological conditions that, in the investigator's opinion, could limit the subject's

ability to participate in the clinical investigation or to comply with follow-up requirements, or impact the scientific soundness of the clinical investigation results

24. Life expectancy <1 year

5.3.2.2 Imaging Exclusion Criteria:

1. Mural thrombus in the left ventricle
2. Documented presence of aortic stenosis (orifice area of 1.5cm² or less)
3. Moderate to severe aortic insufficiency by echocardiographic assessment

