6.8 Additional Information on Required Assessments

Neurological Assessments

In cases of suspected neurological dysfunction, appropriately trained individuals will perform standard neurological examinations and assessments. Subjects who exhibit signs/symptoms of cerebrovascular accident (CVA) or transient ischemic attack (TIA) should have a diagnosis confirmed by appropriate diagnostic imaging.

Echocardiographic Assessments

All subjects will have echocardiograms performed at the following time points:

- 1) Baseline – performed within 60 days prior to the index procedure; required for the analysis of the primary endpoint component (change in aortic insufficiency from baseline to 90 days) and the descriptive endpoints as well as for the assessment of the eligibility requirements (e.g. LVEF <50%, no moderate or severe aortic insufficiency, no aortic stenosis (stenosis as defined by the orifice area of 1.5cm² or less), and no mural thrombus in the left ventricle)
- 2) Post-device removal – no later than 48 hours post-device removal; required for and the descriptive endpoint
- 3) 90 days post-device removal (\pm 30 days) – required for the analysis of the primary endpoint component (change in aortic insufficiency from baseline to 90 days) and the descriptive endpoint
- 4) Unscheduled – if new valvular abnormalities are suspected post device removal, an echocardiogram should be performed and the results documented on the eCRF.

Particular attention should be made to the presence of thrombus and any new abnormalities (or worsening of existing abnormalities) of the aortic valve.

IMPORTANT: All echocardiograms must have a focus on aortic valve (refer to the Echocardiographic Core Laboratory guidance) and must be submitted to the core laboratory for analysis. Both baseline and 90-day echocardiograms are required for the quantitative assessment of change in aortic insufficiency from baseline to 90 days, which is part of the primary endpoint in SHIELD II. For a baseline echocardiogram performed prior to the subject signing informed consent, the investigators will need to assess whether the available baseline echocardiogram captures the appropriate images of aortic valve required for a quantitative assessment of aortic regurgitation by the Echocardiographic Core Laboratory per the Echocardiographic Core Laboratory guidance. If not, a baseline echocardiogram will need to be repeated per the Echocardiographic Core Laboratory guidance before the index procedure.

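### SAP 2.2.2, on its more natural reading, drops from the primary denominator completers already known to be event-free because only the baseline aortic insufficiency grade is missing; the effect is probably small

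*SAP*

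**What the plan says.** SAP 2.3.1 states that the primary endpoint "will be evaluated using the difference in event rates in the ITT population of the pivotal phase". SAP 2.2.2 sets the denominator of that rate. It opens with "The denominator of the primary endpoint event rate will exclude subjects in the analysis population who terminated from the study" (part of the sentence is redacted) and adds a second group: "any subject who completes the 90-day follow-up without aortic insufficiency data at either baseline or 90-day follow-up and without a primary endpoint event". For the AI component on its own, SAP 2.2.2 gives a different instruction: it is a component "which is an imaging endpoint and will follow the denominator rule set forth for missing data handling". The visible part of SAP 2.9 says only that missing data are excluded.

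The AI component is defined in SAP 1.4.1: "Change in aortic insufficiency from baseline to 90 days by echocardiographic assessment and defined as" a three-row table. The rows start from None, Trace and Mild, and all have the same 90-day entry; the last reads "Mild | Moderate OR Severe".

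Two protocol provisions bear on this. Section 5.3.2 lists as an imaging exclusion "Moderate to severe aortic insufficiency by echocardiographic assessment". Section 6.8 says "Both baseline and 90-day echocardiograms are required for the quantitative assessment of change in aortic insufficiency from baseline to 90 days". Sections 6.1 and 6.8 also provide that a baseline echocardiogram obtained before consent is repeated before the index procedure if the investigator finds its aortic valve views unsuitable for core-laboratory quantification.

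**The concern.** The clause treats a missing baseline grade like a missing 90-day grade, but under the plan's own table the two carry different information. Without the 90-day grade, the AI outcome is unknown. Without the baseline grade, the outcome is still fully known whenever the 90-day grade is None, Trace or Mild.

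At stake is the intention-to-treat (ITT) non-inferiority comparison. It would lose subjects whose composite outcome is settled, and nearly all would be non-events, so each arm's rate rises and precision falls. If baseline gradability differed between arms, the difference itself would move. In the other direction, a subject with Moderate or Severe AI at 90 days and no baseline grade fits no row of the table and may drop out. That could hide a possible event in a component that matters for a pump placed across the aortic valve; protocol 15.4 names valve injury and insufficiency as risks of its use.

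**Working it through.** **Step 1. Apply the clause to three completers with no other primary endpoint event.**

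| Completer | Outcome under SAP 1.4.1 | One missing grade excludes | Only two missing grades exclude |
|---|---|---|---|
| A: baseline missing, 90-day Trace | Certain non-event | Dropped | Kept as non-event |
| B: baseline missing, 90-day Severe | Probable event (entry excluded moderate to severe AI) | May be dropped | Kept, but no table row applies |
| C: baseline Mild, 90-day missing | Undetermined | Dropped | Counted as event-free |

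Only C needs missing-data handling. The first reading mishandles A and possibly B; the second mishandles C. Protocol 6.8, which requires both echocardiograms, favours the first.

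**Step 2. Inputs.** From SAP 2.3.1 and 2.4: one-sided alpha 0.025, control rate 20%, margin 10 points, 473 subjects (315 + 158). From SAP 1.5.1: maximum 716, split here as 477 + 239 to respect 2:1. Assumed: 20% in both arms, an unpooled normal test, and a share m of event-free subjects who lack only the baseline grade. The documents do not give m; the range is 0.5% to 5%. Everyone dropped is treated as a non-event (case A), and other losses are ignored.

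**Step 3. The plan's own sample size.** The assumed HeartMate PHP rate, power and attrition are not visible, so 473 cannot be uniquely reproduced. With equal 20% rates, 80% power would need 567. Other plausible inputs come close to 473, for example a PHP rate of 19%, 80% power and 0% to 5% attrition (462 to 487). Nothing here shows 473 to be wrong, and the point does not depend on it.

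**Step 4. Formulas.**
- Dropped = N × 0.80 × m
- Observed rate = 0.20 / (1 − 0.80m)
- SE = √[p(1−p)(1/n₁ + 1/n₂)], with the observed rate p and the reduced n
- Power = Φ(0.10/SE − 1.96)

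With nothing dropped and N = 473: SE = √[0.16 × (1/315 + 1/158)] = 0.0390, and power = Φ(0.604) = 72.7%.

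At m = 5%: dropped = 473 × 0.80 × 0.05 = 18.9; rate = 0.20/0.96 = 20.8%; retained 302.4 and 151.7; SE = 0.0404; power = 69.7%.

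**Step 5. Results.**

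| m | Dropped of 473 | Observed rate | Power, N = 473 | Power, N = 716 |
|---|---|---|---|---|
| 0 | 0 | 20.0% | 72.7% | 88.4% |
| 0.5% | 1.9 | 20.1% | 72.4% | 88.2% |
| 1% | 3.8 | 20.2% | 72.1% | 88.0% |
| 2% | 7.6 | 20.3% | 71.5% | 87.5% |
| 5% | 18.9 | 20.8% | 69.7% | 86.1% |

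**Step 6. Effect on the difference.** With equal m, a true difference of 0 stays 0. True rates of 25% and 20% at m = 5% become 25.97% and 20.83%, so 5.0 points become 5.1. If 5% is missing in one arm and none in the other, the difference moves by 20.83 − 20.00 = 0.8 point; the sign depends on which arm loses more. At 2% versus 1% the shift is 0.16 point.

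**The case against.** The strongest reply is that the trigger should be rare. Baseline echocardiography decides eligibility, randomization follows confirmation of eligibility, and unsuitable pre-consent images are to be repeated. This stands, and it is why the range stops at 5% and the point is graded minor. It does not remove the trigger: the investigator judges suitability, so a subject can be eligible on the site reading and still have no core-laboratory grade.

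A reader might infer that the rule creates a material false difference between arms. The documents do not support that. Baseline imaging precedes treatment, and PCI is to follow randomization promptly. A repeat echocardiogram after open-label assignment is not ruled out, but nothing visible suggests gradability that depends on arm. Heavier loss in the PHP arm would also raise its observed rate and work against non-inferiority.

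A reader might also infer that the outcome of every excluded subject is known. That holds for None, Trace or Mild at 90 days. For Moderate or Severe it is only probable, because a core-laboratory baseline grade could differ from the site's. The visible SAP also does not say that AI data means core-laboratory data. If the site reading counts, such a subject has a baseline grade, is an event, and is never excluded.

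Finally, parts of SAP 2.2.2, 2.3.1, 2.9 and 2.12 are redacted and may already hold a rule. SAP 2.12 names worst-case, tipping-point and multiple-imputation analyses, with details not visible. That limits certainty about the whole plan. It does not change what the visible clause says, and imputation is unnecessary where the outcome is already determined.

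**Conclusion.** The clause gives a wrong result on either reading. On the more natural one it discards certain non-events, and it may discard probable events. On the other it counts an undetermined completer as event-free. The first part follows from the plan's own table and needs no outside assumption.

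The size does rest on assumptions. Within the assumed range for m, equal 20% rates and 315/158, the loss is 2 to 19 subjects and at most about 3 points of power; at 716 the largest loss is about 2.3 points (88.4% to 86.1%). These power levels are illustrative, because the trial's own power assumptions are redacted. The loss of Moderate or Severe cases has not been quantified, and any such events would partly offset the rise in observed rates. The visible documents do not show that the non-inferiority conclusion would change. Severity: minor.

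**What to change.** In SAP 2.2.2, exclude an event-free completer for missing AI data only when the outcome cannot be determined, that is, when the 90-day grade is missing. Then add three statements:

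- A 90-day grade of None, Trace or Mild is scored as no AI event regardless of baseline.
- For a 90-day grade of Moderate or Severe with no core-laboratory baseline grade, the site's eligibility reading serves as baseline. A sensitivity analysis repeats the primary comparison without that substitution.
- The AI component reported alone uses the same derivation.

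If the redacted missing-data text already contains such a rule, SAP 2.2.2 should cross-refer to it. The change should be made before unblinding.

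The cost is some SAP wording and a few lines of derivation code, with no new data. The downside is that a few subjects may rely on a site rather than a core-laboratory baseline reading, which the sensitivity analysis would expose.
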